2.1.2 Prior or concomitant medications

All medications taken within 30 days prior to screening and until end of the study, including COPD controller medications, systemic corticosteroids, and all other medications are to be reported in the case report form (CRF) pages.

All medications will be coded using the World Health Organization-Drug Dictionary (WHO-DD) version currently in effect at Sanofi at the time of database lock.

Prior medications are those the patient used prior to first IMP injection. Prior medications can be discontinued before first administration or can be ongoing during treatment phase.

Concomitant medications are any treatments received by the patient concomitantly to the IMP, anytime from the first administration of IMP to the last administration of IMP + 98 days. A given medication can be classified as a prior medication, concomitant medication and posttreatment medication at the same time.

Posttreatment medications are those the patient took in the period from the last administration of IMP + 99 days to the end of the study.

Any technical details related to computation, dates, imputation for missing dates are described in [Section 2.5](#).

2.1.2.1 COPD controller medication

At Screening Visit 1, all patients must be on triple background therapy, for 3 months prior to Visit 2/Randomization and at a stable dose of medication for at least 1 month prior to the Screening/Visit 1, including triple therapy: LABA + LAMA +ICS (Double therapy: LABA + LAMA allowed if ICS is contraindicated).

Throughout the study, patients should continue their established background therapy for COPD, including dose and regimen.

Patients must be willing to stay on their established background medication for COPD throughout the duration of the treatment period. After successful management of an acute exacerbation of COPD (eg, with oral corticosteroids and/or antibiotics), all efforts should be made to resume the initial background COPD treatment regimen if in the investigator's opinion this is medically acceptable. Background medications should not be adjusted during Screening. After 1 severe or 2 moderate exacerbations of COPD, dose adjustments in background therapy will be permitted for symptom control and as needed for the remainder of the trial period.

Adjustment of background medication is allowed at the discretion of the investigator as clinically indicated during the post-treatment period.

2.1.2.2 Reliever medication

Patients may administer albuterol/salbutamol or levalbuterol/levosalbutamol or ipratropium or ipratropium/short-acting β agonists [SABA] combinations or terbutaline as needed during the study. Nebulizer solutions may be used as an alternative delivery method.

2.1.3 Efficacy endpoints

2.1.3.1 Primary efficacy endpoint

The primary endpoint for this study is the annualized rate of moderate or severe COPD exacerbation (as defined below) over the 52-week treatment period compared to placebo.

Moderate exacerbations are recorded by the Investigator and defined as AECOPD that require either systemic corticosteroids (such as intramuscular, intravenous or oral) and/or antibiotics.

Severe exacerbations are recorded by the Investigator and defined as AECOPD requiring hospitalization, or treatment for >24 hours in emergency department/urgent care facility or result in death.

For both moderate and severe events to be counted as separate events, they must be separated by at least 14 days.

The number of moderate or severe exacerbation events during the 52-week treatment period is defined as the number of moderate or severe exacerbation events with onset during the 52-week treatment period per patient-year. Patients who permanently discontinue the study medication will be asked and encouraged to return to the clinic for all remaining study visits and their additional off-treatment moderate or severe exacerbation events up to Visit 16 (Week 52) will be included.

AECOPD recorded in eCRF will go through a confirmatory adjudication by experts independent of sponsor for the evaluation. Details of the adjudication process are described in the AC Charter/Manual of Operation. Only the adjudicated confirmed AECOPD will be used for analysis.

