Objectives Endpoints Primary To evaluate the efficacy of dupilumab 300 mg Annualized rate of moderate* or severe** COPD exacerbations over q2w in patients with moderate or severe the 52-week treatment period compared to placebo. COPD as measured by *Moderate exacerbations are recorded by the Investigator and Annualized rate of acute moderate defined as AECOPD that require either systemic corticosteroids or severe COPD exacerbation (such as intramuscular, intravenous or oral) and/or antibiotics. (AECOPD). **Severe exacerbations are recorded by the Investigator and defined as AECOPD requiring hospitalization, or observation for >24 hours in an emergency department/urgent care facility or resulting in death. For both moderate and severe events to be counted as separate events, they must be separated by at least 14 days.

Objectives	Endpoints
Key secondary	
To evaluate the effect of dupilumab 300 mg q2w on	 Change in pre-bronchodilator FEV₁ from baseline to Week 12 compared to placebo.
 Pre-bronchodilator forced expiratory volume in 1 second (FEV₁) over 12 weeks compared to placebo. Health related quality of life, assessed by the change from baseline to Week 52 in the St. George's Respiratory Questionnaire (SGRQ). Pre-bronchodilator FEV₁ over 52 weeks compared to placebo. 	 Change from baseline to Week 52 in SGRQ total score compared to placebo. Proportion of patients with SGRQ improvement ≥4 points at Week 52. Change in pre-bronchodilator FEV₁ from baseline to Week 52 compared to placebo.

Overall design:

Multinational, randomized, double-blind, placebo-controlled, parallel group (2 groups), 52-week, pivotal Phase 3 study to assess the efficacy, safety, and tolerability of dupilumab in patients with moderate-or-severe COPD with Type 2 inflammation such as that driven by activation of IL-4, IL-5, and IL-13 on an established long acting beta-agonist (LABA), long acting muscarinic antagonist (LAMA) and/or inhaled corticosteroid (ICS) background therapy (triple therapy unless ICS contraindicated). Study treatments are dupilumab 300 mg q2w or placebo q2w administered during the 52-week randomized treatment period. The study includes 3 study periods.

- Screening (4 weeks ± 1 week).
- Randomized investigational medicinal product (IMP) treatment period (52 weeks ±3 days).
- Post IMP treatment period (12 weeks ± 5 days).

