5.1 INCLUSION CRITERIA

Participants are eligible to be included in the study only if all of the following criteria apply:

Age

I 01. Participant must be ≥ 40 to ≤ 85 years of age, at the time of signing the informed consent.

Type of participant and disease characteristics

- I 02. Participants with a physician diagnosis of COPD who meet the following criteria at screening:
 - Current or former smokers with a smoking history of ≥ 10 pack-years.
 - Current smokers are defined as those patients who are active smokers with ≥10 pack-years of smoking (active smoking includes cigarettes, e-cigarettes, cigars, pipes, etc).
 - Former smokers are defined as those patients who were active smokers with ≥10 pack-years of smoking (active smoking includes cigarettes, e-cigarettes, cigars, pipes, etc) and who have stopped smoking for at least 6 months prior to Visit 1.
 - Moderate to severe COPD (post-bronchodilator FEV₁/FVC ratio <0.70 and post-bronchodilator FEV₁ % predicted >30% and \leq 70%).
 - Medical Research Council (MRC) Dyspnea Scale Grade ≥2.
 - Patient-reported history of signs and symptoms of chronic bronchitis (chronic productive cough) for 3 months in the year up to screening in the absence of other known causes of chronic cough.
 - Documented history of high exacerbation risk defined as exacerbation history of
 ≥2 moderate* or ≥1 severe** within the year prior to inclusion.
 - At least one exacerbation should have occurred while the patient was taking ICS/LAMA/LABA (or LAMA/LABA if ICS is contradicted).
 - * Moderate exacerbations are recorded by the Investigator and defined as AECOPD that require either systemic corticosteroids (intramuscular (IM), intravenous, or oral) and/or antibiotics. One of the two required moderate exacerbations has to require the use of systemic corticosteroids.
 - ** Severe exacerbations are recorded by the Investigator and defined as AECOPD requiring hospitalization or observation >24 hours in emergency department/urgent care facility.
 - Background triple therapy (ICS + LABA + LAMA) for 3 months prior to randomization with a stable dose of medication for ≥1 month prior to Visit 1: (Double therapy: LABA + LAMA allowed if ICS is contraindicated).
- I 03. Evidence of Type 2 inflammation: Patients with blood eosinophils ≥300 cells/microliter at Visit 1 (Screening).

Weight

I 04. Body mass index (BMI) \geq 16 kg/m².

Sex

I 05. Male or Female.

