8.1 EFFICACY ASSESSMENTS

8.1.1 Disease-specific efficacy measures

8.1.1.1 Severity of COPD exacerbations as defined by the protocol

"Moderate exacerbations" are recorded by the Investigator and defined as AECOPD that require either systemic corticosteroids (such as intramuscular, intravenous or oral) and/or antibiotics. "Severe exacerbations" are recorded by the Investigator and defined as AECOPD requiring hospitalization, or observation for >24 hours in emergency department/urgent care facility or resulting in death.

All other exacerbations will be classified as "mild".

For both moderate and severe events to be counted as separate events, they must be separated by at least 14 days.

Clinical symptoms of exacerbations of COPD

In addition to the protocol-defined exacerbations of COPD listed above, clinical signs and symptoms of exacerbations of COPD will be captured in the eCRF (including, but not limited to increase in dyspnea, increase in wheezing, increase in cough, increase in sputum volume and/or increase in sputum purulence).

Management of exacerbations of COPD

Exacerbations of COPD should be treated as deemed necessary by the Investigator. After successful management of an acute exacerbation of COPD (eg, with oral corticosteroids and/or antibiotics), all efforts should be made to resume the initial background COPD treatment regimen if in the Investigator's opinion this is medically acceptable. After 1 severe or 2 moderate exacerbations of COPD, dose adjustments in background therapy will be permitted for symptom control and as needed for the remainder of the trial period.

Protocol defined COPD exacerbation events are collected as efficacy endpoints via the exacerbation eCRF. These events should not be reported as AEs unless they fulfill a seriousness criterion.

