2.1.3.2 Secondary efficacy endpoint(s)

The key secondary endpoints of this study include:

- Change in pre-bronchodilator FEV1 from baseline to Week 12
- Change in pre-bronchodilator FEV1 from baseline to Week 52
- Change in pre-bronchodilator FEV1 from baseline to Week 12 in the subgroup of patients with baseline FeNO ≥ 20 ppb
- Change in pre-bronchodilator FEV1 from baseline to Week 52 in the subgroup of patients with baseline FeNO ≥ 20 ppb
- Change from baseline to Week 52 in SGRQ total score
- Proportion of patients with SGRQ improvement ≥ 4 points at Week 52
- Annualized rate of moderate or severe COPD exacerbation compared to placebo over the 52-week treatment period in the subgroup of patients with baseline FeNO ≥ 20 ppb

Other secondary efficacy endpoints include:

- Change in pre-bronchodilator FEV1 from baseline through weeks other than 12 and 52 (ie, Weeks 2, 4, 8, 24, 36, and 44 compared to placebo)
- Change in post-bronchodilator FEV1 from baseline to Weeks 2, 4, 8, 12, 24, 36 and 52
- Change in forced expiratory flow (FEF) 25-75% from baseline to Weeks 2, 4, 8, 12, 24, 36, 44, and 52
- Annualized rate of severe COPD exacerbations compared to placebo over the 52-week treatment period
- Time to first moderate or severe COPD exacerbation compared with placebo during the 52-week treatment period.

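### The SAP words the emergency-care limb of a severe exacerbation as treatment for more than 24 hours where the protocol says observation; this mainly affects the severe-event endpoints, which are outside the testing hierarchy.

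*SAP*

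**What the plan says.** SAP 2.1.3.1 holds the SAP's only definition of a severe exacerbation. Besides hospitalization, the qualifying routes are "or treatment for >24 hours in emergency department/urgent care facility or result in death".

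Protocol 8.1.1.1 gives the same routes with one word changed: "or observation for >24 hours in emergency department/urgent care facility or resulting in death". The protocol synopsis and Table 1 also say "observation for >24 hours in an emergency department/urgent care facility or resulting in death". Inclusion criterion I 02, which governs the exacerbation history at entry, reads "AECOPD requiring hospitalization or observation >24 hours in emergency department/urgent care facility".

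The rest of the definition agrees. Both documents include hospitalization and death, and both require 14 days between separate events. A moderate event is defined in both as "AECOPD that require either systemic corticosteroids (such as intramuscular, intravenous or oral) and/or antibiotics". Protocol 8.1.1.1 classes every other exacerbation as mild, and mild events are outside the primary composite.

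SAP Table 1 in Section 1.5 lists only the added interim analysis as a statistical change, and SAP 1.6 declares no modification made in the SAP itself.

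**The concern.** Observation for more than 24 hours can be met by length of stay. Treatment for more than 24 hours asks how long therapy was given. A patient treated on arrival and then watched past 24 hours without admission meets the first condition but arguably not the second. The emergency-only route is one the plan provides for: SAP 2.1.1 tabulates prior severe exacerbations handled by an emergency visit alone, separately from those admitted.

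The SAP lists "Annualized rate of severe COPD exacerbations compared to placebo over the 52-week treatment period" among its other secondary endpoints, and Section 2.4.4.5.2 adds time to first severe exacerbation as an exploratory analysis. Both depend directly on the severe definition. The primary endpoint depends on it only through events that are not already moderate. With two wordings and no declared change, the severe count could be derived in either of two ways, and the choice could be questioned after unblinding.

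**Working it through.** **1. Which events the wording separates.** A patient treated for more than 24 hours in the facility has also been there for more than 24 hours, so the SAP wording is the narrower one. Take an event with an emergency stay of more than 24 hours, no admission and no death:

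| Event | Protocol | SAP wording | In primary composite under SAP? |
|---|---|---|---|
| A. Treated for more than 24 h, by any therapy | Severe | Severe | Yes |
| B. Treated for 24 h or less; needed systemic corticosteroids and/or antibiotics | Severe | Moderate | Yes |
| C. Treated for 24 h or less; needed neither drug class | Severe | Neither moderate nor severe | No |

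B and C both leave the severe-event endpoints. Only C leaves the primary composite.

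**2. Where the affected endpoints sit.** The hierarchy in SAP 2.4.4.3 contains neither the severe-event rate (SAP 2.4.4.4.4) nor time to first severe exacerbation (SAP 2.4.4.5.2).

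**3. History covariate.** The primary model (SAP 2.4.4.1) uses the number of moderate or severe events in the prior year, grouped as 2 or fewer, 3, or 4 or more. Moving an event from severe to moderate does not change that number.

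**4. The plan's own sample size.** Inputs from Protocol 9.2: placebo rate 1.5 per year, rate ratio 0.75 (dupilumab rate 1.125), mean duration 0.95 year, dispersion 1, two-sided alpha 0.05, power 90%.

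n per arm = (z for alpha + z for power)² × V / (ln RR)², with V = 1/(t·r0) + 1/(t·r1) + 2k.

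- V = 1/(0.95 × 1.5) + 1/(0.95 × 1.125) + 2 = 0.7018 + 0.9357 + 2 = 3.6374
- (1.9600 + 1.2816)² = 10.507; (ln 0.75)² = 0.08276
- n = 10.507 × 3.6374 / 0.08276 = 461.8, so 462 per arm and 924 in total, as stated
- Power with 462 per arm: 90.0% at alpha 0.05 and 89.9% at alpha 0.049, as stated

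**5. Scale for the primary (assumption, not a figure from the documents).** Suppose events of type C are a share s of all events, lost equally in both arms, with the rate ratio and dispersion unchanged. The placebo rate becomes 1.5 × (1 − s).

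| s | Placebo rate | Power, alpha 0.05 | Power, alpha 0.049 |
|---|---|---|---|
| 0% | 1.500 | 90.0% | 89.9% |
| 1% | 1.485 | 89.9% | 89.7% |
| 2% | 1.470 | 89.7% | 89.6% |
| 5% | 1.425 | 89.3% | 89.2% |
| 10% | 1.350 | 88.6% | 88.4% |

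Worked row, s = 5%: V = 0.7387 + 0.9849 + 2 = 3.7236; standard error = √(3.7236/462) = 0.08978; 0.28768/0.08978 − 1.9600 = 1.2445, which gives 89.3%.

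No similar calculation is possible for the severe-event endpoints. The documents give neither a severe-event rate nor the share of severe events that qualify through an emergency stay alone.

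**The case against.** The strongest reply is that this is a loose paraphrase with no operational effect. Both documents say the investigator records severe events, and investigators work from the protocol. Only adjudicated, confirmed events are analysed, and the SAP describes no step that re-derives severity from hours of treatment. This largely stands as to what will probably happen: the documents do not show that a second rule would be applied to the data. They do not rule it out either, because the adjudication charter and the eCRF derivation are not among them, and the SAP is the document from which the analysis is programmed.

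A second reply is that Protocol Appendix 3 describes hospitalization broadly enough to include being kept on an emergency ward for observation or treatment. On that reading some of these stays would already be severe through the hospitalization limb, which is common to both documents. This stands in part. It is guidance for classifying serious adverse events, and the endpoint definition lists emergency stays as a separate route.

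Three stronger readings are tempting and not supported:

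- A reader might infer that any event observed for more than 24 hours without systemic corticosteroids or antibiotics disappears under the SAP. It does not. Those drugs define a moderate event; the severe limb says treatment without naming a therapy, so more than 24 hours of, for example, nebulized bronchodilator would still qualify.
- A reader might infer that baseline and on-study severity enter the primary model under different rules. The covariate pools moderate and severe events, so it is essentially unaffected.
- A reader might infer that the primary result or the sample size is undermined. The sample size reproduces, and even an assumed 10% loss of events costs about 1.4 percentage points of power (90.0% − 88.6%).

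**Conclusion.** The mismatch is real, exact and undeclared, and it concerns one limb of one definition. Its consequence is a possible severe-versus-not-severe classification difference for emergency stays of more than 24 hours with 24 hours or less of treatment, no admission and no death. It bears mainly on the annualized rate of severe exacerbations (other secondary) and time to first severe exacerbation (exploratory), and no alpha-controlled test depends on either. For the primary composite only the type C events matter, and the effect is probably very small.

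The size cannot be derived from the documents. The power range above assumes equal loss in both arms with the rate ratio and dispersion unchanged. Whether any event would actually be reclassified depends on the charter and the eCRF derivation. This is a consistency point that should be settled before the interim lock; it is not a threat to the trial's primary conclusion.

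**What to change.** In SAP 2.1.3.1, replace *treatment* with *observation* in the emergency-care limb, so that it matches the protocol's endpoint definition. At the same time, confirm that the adjudication charter and the eCRF severity derivation use that wording. If treatment was the intended criterion, declare and justify the change in SAP 1.6 and apply it in all three places.

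Do this before the interim database lock, the point by which Protocol 9.4 requires the SAP to be final. The cost is one word in the SAP and a check of two supporting documents. Sample size, alpha and trial procedures do not change.

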2.1.3.2 Secondary efficacy endpoint(s)

The key secondary endpoints of this study include:

- Change in pre-bronchodilator FEV1 from baseline to Week 12
- Change in pre-bronchodilator FEV1 from baseline to Week 52
- Change in pre-bronchodilator FEV1 from baseline to Week 12 in the subgroup of patients with baseline FeNO ≥ 20 ppb
- Change in pre-bronchodilator FEV1 from baseline to Week 52 in the subgroup of patients with baseline FeNO ≥ 20 ppb
- Change from baseline to Week 52 in SGRQ total score
- Proportion of patients with SGRQ improvement ≥ 4 points at Week 52
- Annualized rate of moderate or severe COPD exacerbation compared to placebo over the 52-week treatment period in the subgroup of patients with baseline FeNO ≥ 20 ppb

Other secondary efficacy endpoints include:

- Change in pre-bronchodilator FEV1 from baseline through weeks other than 12 and 52 (ie, Weeks 2, 4, 8, 24, 36, and 44 compared to placebo)
- Change in post-bronchodilator FEV1 from baseline to Weeks 2, 4, 8, 12, 24, 36 and 52
- Change in forced expiratory flow (FEF) 25-75% from baseline to Weeks 2, 4, 8, 12, 24, 36, 44, and 52
- Annualized rate of severe COPD exacerbations compared to placebo over the 52-week treatment period
- Time to first moderate or severe COPD exacerbation compared with placebo during the 52-week treatment period.

2.1.3.2.1 Key secondary endpoint

2.1.3.2.1.1 Spirometry

Spirometry at clinical site visits should be performed in accordance with the European Respiratory Society (ERS)/American Thoracic Society (ATS) guidelines ([1](#)) and prior to administration of investigational product.

For pre-bronchodilator measured parameters, including FEV₁, FVC and forced expiratory flow (FEF) 25%-75%, spirometry will be performed after a wash out period of bronchodilators according to their action duration, for example, withholding the last dose of salbutamol/albuterol or levosalbutamol/levalbuterol for at least 6 hours, withholding the last dose of LABA for at least 12 hours (ultra-long acting LABA like vilanterol should be withheld for at least 24 hours), withholding the last dose of ipratropium for at least 8 hours and withholding the last dose of LAMA for at least 24 hours. This will be verified before performing the measurements.

Note: When both pre- and post-bronchodilator spirometry is assessed, the post-bronchodilator spirometry should be performed consistent with the mechanism of action of reliever (ie, 30 minutes for albuterol or another SABA).

At all visits, spirometry will be performed preferably in the morning; afternoon/evening is allowable in the exceptional circumstance when morning spirometry cannot be performed; spirometry should be done at approximately the same time at each visit throughout the study. Current smokers need to be reminded not to smoke for at least 1 hour before spirometry. The same spirometer and standard spirometric techniques, including calibration, will be used to perform spirometry at all visits and, whenever possible, the same person should perform the measurements.

Three measurements fulfilling the ATS acceptability and repeatability criteria should be obtained at every visit, if possible.

2.1.3.2.1.2 St. George's Respiratory Questionnaire (SGRQ)

The St. George's Respiratory Questionnaire (SGRQ) ([2](#), [3](#)) is a 50-item questionnaire designed to measure and quantify health status in adult patients with chronic airflow limitation (see Appendix B).

Scores by dimension are calculated for three domains: Symptoms, Activity and Impacts (Psychosocial) as well as a total score. Global and domain scores range from 0 to 100, with 100 representing the worst possible health status and 0 indicating the best possible health status. See St. George's Respiratory Questionnaire manual Version 2.3 page 8-13 (Appendix C) for the scoring algorithm.

The first part ("Symptoms") evaluates symptomatology, including frequency and severity of cough, sputum production, wheeze, breathlessness and the duration and frequency of attacks of breathlessness or wheeze. The second part has two components: "Activity" and "Impacts". The "Activity" section addresses disturbances to patients' daily physical activities. The "Impacts" section covers a range of effects that chest troubles may have on patients' daily life and psychosocial functions (eg, daily life activities and functioning, employment, physical functioning, emotional impact, stigmatization, and patients' perceptions when treated). The recall period of the questionnaire is over the past 4 weeks.

Psychometric testing has demonstrated its repeatability, reliability and validity. Sensitivity has been demonstrated in clinical trials. A minimum change in score of 4 units was established as clinically relevant after patient and clinician testing (4, 5). The SGRQ has been used in a range of disease groups including asthma, COPD and bronchiectasis.

SGRQ is assessed at Visit 2 (Week 0), Visit 4 (Week 4), Visit 6 (Week 12), Visit 9 (Week 24), Visit 12 (Week 36), Visit 16 (Week 52), and Visit 19 (Week 64).

